Cover page

Title of study

Maternal role in sensory motor stimulation for Oral Feed Establishment in preterm neonates: MSMS trial

NCT number

NCT05484726

Date of document

21 April 2024

Maternal role in sensory motor stimulation for Oral Feed Establishment in preterm neonates: MSMS trial

Oral feed establishment is one of the most challenging milestones for preterm neonates. It is becoming an emerging challenge for neonatologists with an improvement in the survival of preterm neonates. A successful transition from full gavage (tube) feeding to independent oral feeding is considered an important milestone of neonatal neurodevelopment maturation. It has been estimated that about 40% of preterm neonates face difficulty transitioning from gavage to oral feeding (1).

Tube feeding-related problems are commonly observed in neonates. A literature review regarding the safety profile of having a feeding tube shows that it is not risk-free. Major problems enlisted are mechanical, functional, nutritional, biological and neurodevelopmental (mental motor delay) (2-5).

According to Heidelise Als' "Synactive Theory" in growing fetus and neonate, developmental maturation is done by integrating neonatal internal physiological status and functional demands with multisensory inputs from the environment (6,7). In preterm neonates, synergistic effects of combined oral and non-oral sensorimotor (tactile/kinesthetic) interventions have shown promising results (8). It helps augment their experience to exercise their innate (sucking) reflex that ultimately decreases transition time from introduction to safe full independent oral feeding (9). Feeders and grower neonates are ideal for oral stimulation for oral feed establishment.

The ideal time to start oral feeding in preterm neonates is still debatable. In developing fetus shows sucking, swallowing and breathing at 15, 14 and 10 weeks of gestation, respectively (10). Feeding development undergoes maturational processes throughout gestation, from non-coordinated sucking and swallowing movements to fully coordinated suck-swallow-breathe, usually occurring after 34 weeks. Unlike the term sucking reflex, preterm neonates have a predominant expression pattern of sucking with no suction. Lau et al. demonstrated that around 30 weeks of post-menstrual age (PMA), healthy preterm neonates could complete their successful oral feeding within 20 minutes using an immature sucking reflex (11).

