However, all those neonates having major anomalies incompatible with life, major malformations, syndromic babies, cleft lip and palate, genetic disorders, haemodynamically unstable babies including IVH (grade III & IV), haemodynamically significant PDA (HsPDA) requiring antifailure therapy, NEC (stage II & III) or anemia requiring blood transfusion. All those neonates with adverse events including cough with choking, breath holding, choking, aspiration, tachycardia HR > 200/min, bradycardia HR < 100/min, apnea > 15 sec, tachypnea RR > 70/min while stimulation or feeding were excluded.

Protocol

Interventional Study Model: Factorial Assignment

- Maternal involvement in perioral sensory-motor stimulation be in three stages
 - Observer status
 - Performing under supervision
 - Independent
- Intervention period: 5 days as
 - Training phase (T): T1 and T2 (for mothers by the nurse)
 - Direct feeding phase (D): F1, 2, and 3 (oral feed was offered to neonate)
- Stimulation for 7 minutes and 15 minutes before feeding twice a day at 1100 and 1700 hrs.
- Two groups
 - Intervention group (G I): by mothers
 - Control group (G II): by staff nurses

Number of Arms: 2

Masking: Single (Care Provider)

The mothers, medical staff involved in general care, nursing staff involved in the intervention, and doctors conducting the assessment of oral feeding skills (OFS) were all blinded to allocation. The nursing staff was informed at the time of intervention that participating infants received either sensory motor stimulation or sham oral stimulation depending on group allocation.

Allocation

Randomization was done using a random Alloc Software environment. Gestation age-based stratification was done using 3 blocks design of 28 to 30, 30+1 to 32 & 32+1 to 34. Random allocation of neonates into the intervention or control groups by stratum using lottery method.

Blinding

The mothers, medical staff involved in general care, nursing staff involved in intervention and doctors conducting the assessment of oral feeding skills (OFS) were all blinded to allocation. The nursing staff was informed at the time of intervention that participating infants received either sensory motor stimulation or sham oral stimulation depending on group allocation.

Sample size

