- Hemodynamically significant patent ductus arteriosus (HsPDA) diagnosed by echocardiography
- Necrotizing enterocolitis (NEC) diagnosed using modified Bell's scoring (stage 1)
- Feeding intolerance diagnosed as aspirates > 20% of previous feed ± abdominal distension of > 2cm from base line
- Sepsis (leukocytosis or leukopenia or ANC<150 along with raised CRP and platelets <100 and or positive blood culture)
- Seizures
- Discharge weight in kg
- Duration of stay in NICU in days
- Neonatal feeding characteristics at time of enrollment in study include
 - Postmenstrual age (PMA) measured in weeks
 - Chronological age (ChA) measured in weeks
 - Time/duration to achieve full gavage/tube feed measured in days
 - Daily milk intake (ml/kg/day) when sensory motor stimulation was started
 - Volume of feed prescribed for each feed (ml)

The **outcome** measured were documented daily twice a day (11.00 and 17.00 hrs) until achievement of full oral feed. Full oral feed was volume of 120-140ml/kg/day taken orally. However, to make calculations concise, for both groups, all outcome parameters were documented on proforma for fixed time (11.00 am) for D1, D2, D3, D5, D7 and D14.

- Primary Outcome Measure
 - Transition time to full oral feeding is the time interval between commencement of perioral sensory stimulation on D1 to establishment of full oral feed in both groups. It was done daily till 14th day of perioral sensory motor stimulation. Transition time to full oral feeding was the day at which baby was able to take oral feed of volume of 120-140ml/kg/day.
 - Improvement (change) in efficiency oral feed establishment in terms of amount and time. It was classified into four levels depending upon the level of maturity in ascending order as follows:
 - Level 1: PRO < 30% and RT < 1.5 ml/min
 - Level 2: PRO < 30% and RT ≥ 1.5 ml/min
 - Level 3: PRO ≥ 30% and RT < 1.5 ml/min
 - Level 4: PRO ≥ 30% and RT ≥ 1.5 ml/min

For our RCT, efficacy was measured as the achievement of L4 for the intervention group vs the control group.

- Adverse outcome monitoring was done for every neonate from first day of enrollment in study (D1) till establishment of full oral feed (by D14 expected). These include non-life threatening adverse events including cough, tachycardia HR 180-200/min, bradycardia HR120 - 100/min, , tachypnea RR 60 - 70/min while maintaining SpO2 of >90% at room air
- Secondary Outcome Measure:
 - Total volume (TV) taken during each feed

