 - Volume taken during the first 5 min (TV₅) out of total feed taken orally
 - Rate of transfer (RT) ml/min i.e., how long it neonate takes to finish oral feed.
 - Overall transfer (OT percent) volume taken/total volume prescribed. It shows trend towards oral feed establishment.
 - Proficiency (PRO percent) volume taken during the first 5 min/total volume prescribed.
 - SSB (Suck Swallow Breaths) coordination coordinated, developed pattern of suck swallow and breathe. It is a subjective assessment.

Statistical analysis

The statistical software IBM SPSS Statistics version 21 (SPSS, Chicago, IL) was used for the statistical analysis of the data. Appropriate bivariate analysis was performed to identify the unadjusted differences between the cases and controls. Categorical variables were expressed as frequencies and percentages. According to Shapiro Wilk test all continuous variables were asymmetrically distributed. Mann–Whitney U test was used for nonparametric continuous variables and were described as medians and inter quartile range (IQR). Fisher exact/Chi square test was used to compare categorical variables. Mann-Whitney test was used to compare continuous variables. The p-value of < 0.05 was taken as statistically significant.

Results

During the research period, 1009 newborns were admitted to the Neonatal Intensive Care Unit (NICU). Among them, 142 were born prematurely, with gestational ages falling between 28 and 34 weeks. Out of the preterm neonates, a total of 130 were eligible for the study, as 12 had to be excluded for various reasons. These exclusions included 2 cases where mothers experienced serious postnatal complications, 1 instance of parental refusal to participate, 1 case with incomplete data, and 8 cases that did not meet the inclusion criteria due to different reasons such as syndromic features, cleft lip and palate, suspected inborn error of metabolism (IEM), intraventricular hemorrhage (grade IV), and hemodynamically significant patent ductus arteriosus (HsPDA). Consequently, 130 neonates were included in the study and randomly assigned, with 65 in each group for intervention and control. Sensory motor stimulation (SMS) was administered to 107 of these neonates, and the study was completed with 97 neonates (as illustrated in Figure 1).

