The sociodemographic and clinical characteristics of both mothers and neonates are shown in Table 1. There were no statistically significant differences between groups regarding maternal age, gravidity, education, previous preterm neonates, job status and pregnancy related issues (hypertensive disorder of pregnancy, gestational diabetes, and anemia). Similarly, neonatal characteristics regarding gender, mode of delivery, gestation age, birth weight, weight for gestation age, place of delivery, need and duration of invasive mechanical ventilation (IMV), non

invasive ventilation (NIV) and low flow nasal cannula (LFNC), apnea, RDS, use of caffeine, HsPDA, NEC stage 1, feed intolerance, sepsis, and seizures. (Table 1).

There was also no significant difference in feeding characteristics. The feeding characteristics assessed were postmenstrual (PMA), chronological (ChA) age, and weight at enrollment, time to full gavage feed establishment, amount of milk feed advised for each feed and day on D1, D2, D3, D5, D7 and D14. (Table 2).

Table 3 provides an overview of both the primary and secondary outcomes observed in both study groups. When examining the primary outcome measures, there were no significant differences observed in terms of the time it took to establish full oral feeding, adverse events, or the effectiveness observed during oral assessments. The findings indicate that neonates in the experimental group demonstrated oral feeding skills that were comparable to those in the control group. These skills were measured in terms of volume (both total and during the initial 5 minutes of feeding), feeding rate, overall transfer, proficiency, and the coordination of suck, swallow, and breath (Table 3).

References:

1. da Rosa Pereira K, Levy DS, Procianoy RS, Silveira RC. Impact of a pre-feeding oral stimulation program on first feed attempt in preterm infants: Double-blind controlled clinical trial. *PLoS One*. 2020 Sep 9;15(9):e0237915. doi: 10.1371/journal.pone.0237915. PMID: 32903261; PMCID: PMC7480839.

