Seizures ^a	7 (58.3%)	5 (41.7%)	0.394		
M A T E R N A L	Age ^b	29 (26 - 32)	30 (26.5 – 33)	0.138	
	Gravidity ^a	Primigravida	20 (43.5%)	26 (56.5%)	0.350
		2-3	22 (59.5%)	15 (40.5%)	
		≥ 4	7 (50.0%)	7 (50.0%)	
	Education ^a	Uneducated	2 (50.0%)	2 (50.0%)	0.699
		Primary	11 (52.4%)	10 (47.6)	
		Secondary	15 (42.9%)	20 (57.1%)	
		Higher	21 (56.8%)	16 (43.2%)	
	Previous preterm (yes) ^a	42 (52.5%)	38 (47.5%)	0.281	
	Job status (Housewife) ^a	29 (48.3%)	31 (51.7%)	0.368	
Hypertensive disorder ^a	29 (47.5%)	32 (52.5%)	0.290		
DM ^a	17 (50.0%)	17 (50.0%)	0.555		
Anemia ^a	25 (54.3%)	21 (45.7%)	0.304		

Table 2 : Feeding characteristics

Feeding characteristics	Experimental group (n=49)	Control group (n = 48)	p-value
PMA at enrollment (week)	32 (31 – 33)	32 (31 – 33)	0.787
ChA at enrollment (days)	13 (6 – 14)	9 (7 – 16)	0.925
Time to full gavage feed (days)	7 (5.5 – 13.5)	7 (6 – 14)	0.726
Discharge weight (kg)	1.48 (1.42 – 1.66)	1.48 (1.43 – 1.75)	0.698
Weight at enrollment (kg)	1.35 (1.25 – 1.54)	1.35 (1.21 – 1.60)	0.610
Duration of stay in NICU (days)	21 (15 – 29.5)	30 (16 – 30.75)	0.848
Milk Feed (ml/kg/day)			
Milk feed D1	120 (120 – 120)	120 (120 – 120)	0.302
Milk feed D2	120 (120 – 140)	120 (120 – 140)	0.871
Milk feed D3	140 (140 – 140)	140 (140 – 157.50)	0.109
Milk feed D5	150 (150 – 160)	160 (150 – 160)	0.361
Milk feed D7	160 (160 – 160)	160 (160 – 160)	0.184
Milk feed D14	160 (160 – 180)	160 (160 – 180)	0.758
Volume of feed prescribed (ml/feed)			
Volume prescribed D1	14 (12 – 15.5)	14 (12 – 16)	0.670
Volume prescribed D2	14 (12 – 17.5)	12.5 (12.25 – 19)	0.825
Volume prescribed D3	16 (14 – 17.5)	14 (14 – 20)	0.569
Volume prescribed D5	17 (15 – 19)	17 (15 – 21)	0.758
Volume prescribed D7	18 (16 – 20.5)	18 (16 – 22)	0.614
Volume prescribed D14	18 (16 – 22)	18 (16 – 24)	0.933

Table 3 : Study outcome

Outcome		Experimental gp (n=49)	Control gp (n=48)	p-value
Time to full oral feed (days)		10 (7 – 13)	9 (7 – 13)	0.531
Adverse events	D1	36 (53.7%)	31 (46.3%)	0.234
	D2	14 (50.0%)	14 (50.0%)	0.563
	D3	12 (50.0%)	12 (50.0%)	0.570
	D5	2 (100%)	0 (00%)	0.253
	D7 & 14	0 (00%)	0 (00%)	NA
L4 Efficacy on	D 1 -3	0 (00%)	0 (00%)	NA
	D5	12 (57.1%)	9 (42.9%)	0.331
	D7	16 (51.6%)	15 (48.4%)	0.528
	D14	35 (49.3%)	36 (50.7%)	0.434
Volume Taken Each feed	D1	2.0 (2.0 -7.0)	2.0 (2.0 -7.0)	0.803
	D2	5.0 (2.0 - 9.0)	3.0 (2.0 – 7.0)	0.558
	D3	7.0 (3.0 – 11)	4.0 (3.0 – 10.0)	0.540
	D5	8.0 (5.0 – 15)	6.5 (5.0 – 15)	0.521
	D7	9.0 (7.0 – 18)	7.5 (7.0 – 20)	0.951

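### No outcome comparison adjusts for postmenstrual age at enrollment or for the gestational-age stratum, so a trial that claims sameness gives up some precision or power

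*Combined protocol and SAP*

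**What the plan says.** The introduction states that "Feeding development undergoes maturational processes throughout gestation" and places "fully coordinated suck-swallow-breathe, usually occurring after 34 weeks". The Outcome section grades efficiency of oral feeding on four levels ordered by maturity.

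The Baseline measures section lists "Postmenstrual age (PMA) measured in weeks" under feeding characteristics at enrollment. Weight at enrollment is not in that list, but it was recorded: the Results say "The feeding characteristics assessed were postmenstrual (PMA), chronological (ChA) age, and weight at enrollment", and Table 2 reports it by arm.

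Under Allocation, "Gestation age-based stratification was done using 3 blocks design of 28 to 30, 30+1 to 32 & 32+1 to 34".

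The Statistical analysis section describes the comparisons as bivariate and the differences as unadjusted. For continuous outcomes, "Mann-Whitney test was used to compare continuous variables"; for categorical outcomes it names Fisher's exact or the chi-square test. No regression, stratified test or covariate-adjusted estimate is planned. Table 3 gives medians with IQRs, or counts, each with a p-value and no confidence interval.

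**The concern.** The stated hypotheses are of sameness: mother-delivered stimulation should do as well as nurse-delivered stimulation. The Results conclude that skills were comparable. Such a conclusion is only as strong as the interval for the difference is narrow.

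By the documents' own account, maturity at the start should help predict how soon an infant feeds fully by mouth. The IQR of PMA at enrollment is 31 to 33 weeks in both arms, which lies before the point at which coordination is said to be complete. If PMA predicts outcome, leaving it out leaves explainable variation in the error term. The same holds for the gestational-age stratum, which was important enough to stratify on but does not appear in the analysis.

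**Working it through.** **Is there a figure in the plan to reproduce?** No. The documents give no interval width, margin or covariate–outcome correlation. The planned sample size of 46 does not enter this calculation.

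**Inputs**
- Analysed infants: 49 and 48, total 97 (Sample size; Table 3).
- Transition time: 10 (7–13) and 9 (7–13) days, p = 0.531 (Table 3).
- PMA at enrollment: 32 (31–33) in both arms, p = 0.787. Weight at enrollment: medians 1.35 and 1.35 kg, p = 0.610 (Table 2).
- R² for the covariates: not given, so a range is shown as an assumption.

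**Step 1: unadjusted precision.** By the normal approximation, SD ≈ IQR/1.349 = (13 − 7)/1.349 = 4.45 days. SE = 4.45 × √(1/49 + 1/48) = 0.90 days. The 95% half-width is 1.96 × SE = 1.77 days.

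**Step 2: effect of adjustment.** In a linear model with k covariates and n = 97,

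Var(adjusted)/Var(unadjusted) = (1 − R²) × [1 + k/(n − k − 3)].

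For k = 2 the bracket is 1 + 2/92 = 1.022, an inflation of about 2%. Break-even is at R² = 1 − 1/1.022 ≈ 0.02.

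| Assumed R² | Variance factor | 95% half-width (days) | Equivalent total N |
|---|---|---|---|
| 0 (unadjusted) | 1 | 1.77 | 97 |
| 0.02 | 1.001 | 1.77 | 97 |
| 0.05 | 0.971 | 1.74 | 100 |
| 0.10 | 0.920 | 1.70 | 105 |
| 0.20 | 0.817 | 1.60 | 119 |
| 0.30 | 0.715 | 1.50 | 136 |

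**Step 3: the model recommended below.** Three gestational-age strata need two indicators. With PMA, k = 3, the bracket is 1 + 3/91 = 1.033, and break-even is at R² = 1 − 1/1.033 ≈ 0.03. At R² = 0.20 the half-width is 1.77 × √(0.80 × 1.033) = 1.61 days, against 1.60 with k = 2. The extra term hardly matters.

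**Step 4: the other tested primary outcome.** L4 at D14 is 35/49 = 71.4% against 36/48 = 75.0%, a difference of −3.6 percentage points. SE = √(0.714 × 0.286/49 + 0.75 × 0.25/48) = 0.090, so the unadjusted 95% CI is about −21 to +14 points. This shows how wide the intervals are. The documents give no basis for calculating how far adjustment would narrow this one.

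**The case against.** Unadjusted comparison is valid under randomisation, and the size of the loss is assumed rather than shown. At R² = 0.10 the half-width shrinks by 0.07 days, under two hours, on an outcome counted in days. No margin is stated, so no conclusion can be shown to change. All of this stands, and it limits how much weight the point carries.

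Several stronger readings are tempting, but the documents do not support them.

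- *The arms differ in starting maturity, so the comparison is biased.* A reader might infer this from the chronological-age medians of 13 and 9 days in Table 2. The p-value for that row is 0.925, and PMA and weight at enrollment have the same medians in both arms. No imbalance in starting maturity is visible.
- *Infants in one gestational-age band start more than a week apart in maturity.* The chronological-age IQRs (6–14 and 7–16 days) are pooled over all three bands. Stimulation could not begin before 30 weeks PMA, so infants born earliest had to wait longer, and chronological age partly reflects band. No within-band spread is reported.
- *Weight is as well supported a predictor as PMA.* The introduction argues from gestation and PMA, not weight. Full oral feed is defined per kilogram, and proficiency and overall transfer divide by prescribed volume. There is still some case for weight, because volume taken and the L4 rate threshold are absolute, and prescribed volume scales with weight.
- *Any adjusted model would narrow the interval as in the table.* The half-widths are for a linear mean difference with an approximate SD, while the document says all continuous variables were asymmetrically distributed. In Cox or logistic models the gain is mainly in power, and conditional standard errors need not shrink.

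PMA is gestational age plus chronological age, so PMA and the stratum overlap and the second to enter will add less than the first.

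**Conclusion.** The point holds as one of precision or power, not of bias or validity. Every outcome comparison ignores both a collected variable that the documents treat as driving the outcome and the stratification factor. Under the linear approximation the loss is negligible near R² = 0.02, about 8% of the variance at R² = 0.10, 18% at 0.20 and 29% at 0.30. Which of these applies cannot be settled from the documents. The result rests on SD ≈ IQR/1.349, on 49 and 48 infants, and on the assumed R².

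Adjustment is worth doing because it costs almost nothing and the claim is one of similarity. It would not repair the analysis of 97 of the 130 infants randomised, or supply the missing margin.

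**What to change.** Add adjusted estimates with 95% confidence intervals for transition time and L4, from models with arm, gestational-age stratum and PMA at enrollment as a continuous term. Check collinearity between stratum and PMA. It blurs their separate coefficients, but those are not of interest here. Weight at enrollment, reported in Table 2, is an optional further covariate.

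- **L4:** report a standardised risk difference.
- **Transition time:** report an adjusted difference in days or a Cox model. Say how infants not fully orally fed by day 14 are handled, since follow-up of this outcome ends there. If Cox is used, note that it gains mainly power and need not give a narrower interval.
- **Status:** keep the Mann-Whitney and Fisher/chi-square results as reported, and label the adjusted analysis post hoc, because results are already in the document.

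The covariates are already recorded, so no new data are needed. The cost is about 2% variance inflation with two covariates, or 3.3% with the stratum as two indicators plus PMA, together with a little more analysis and reporting work.

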The sample size was 46 (23 each in interventional and control groups) and calculated with a 95% confidence level, 10% margin of error and 5% level of significance by taking feeding-related problems as 40%. It was done by using openepi.com.

Initially only 46 neonates were enrolled in study. But later an immense maternal response was observed. Mothers were ready to learn and involve in sensory motor stimulation of their neonates. Hence, the final total study population size was 97 with 49 in experimental and 48 in control group.

Procedure of intervention

- The study intermediation was started not before 30 weeks of postmenstrual age when full gavage feeding was established with the addition of supplements.
- All mothers in this study was involved in gavage feeding before involvement in the procedure.
- Trained nurses taught details of sensory-motor stimulation to mothers in easily understandable languages (annexure 1 in (a) English and (b) Urdu). This procedure has been adapted from modified from PIOMI and Fucile (14,15).
- Stimulation was done for 7 minutes and at least 15 minutes before feeding twice daily at 1100 and 1700 hrs till full oral feed establishment (expected time 28 days chronological age)
- Oral feeding was offered using a bottle with a slow-flow nipple.
- Time monitoring for feeding was strictly followed
- Infants was fed for a maximum of 20 min, and feeding was discontinued early if adverse events occur.

Arms and intervention

- Study groups for sensory motor stimulation (5 minutes) + pacifier (2 minutes)
 - Intervention group (G1) : by mothers
 - Control group (G 2) : by staff nurses

Experimental: Intervention group (Group 1)

- Maternal involvement was done in three stages for the intervention group as
 - Observer status
 - T1: Nurses performing all steps while mother observer status
 - T2: Nurses perform all steps in front of the mother and a pacifier was offered by the mother
 - Performing under supervision
 - D1: Mother performs all steps and oral milk was offered by the nurse while the mother observes.
 - D2: Mother performing all steps and offering oral milk while the nurse is supervising

- Independent
 - D3: Mother performing all steps independently
- Study groups for sensory motor stimulation
 - Assigned intervention perioral sensory motor stimulation Step 1 - 6 over 5 minutes + pacifier 2 minutes for total duration of 7 minutes.

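### Adverse events are reported as a primary outcome, but the stated rule keeps one reading on each of six days out of twice-daily records, and no per-infant count is given

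*Combined protocol and SAP*

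**What the plan says.** Under Data Collection, outcomes were "documented daily twice a day (11.00 and 17.00 hrs) until achievement of full oral feed". The next sentences define full oral feed and then, for brevity of calculation, narrow the data: "all outcome parameters were documented on proforma for fixed time (11.00 am) for D1, D2, D3, D5, D7 and D14", in both groups alike. No missing data or clinical reason is given for the narrowing.

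The adverse-event item comes before the secondary outcome list and has its own window: "Adverse outcome monitoring was done for every neonate from first day of enrollment in study (D1) till establishment of full oral feed", expected by D14. It covers non-life-threatening events only. The Results place adverse events under the primary label: "examining the primary outcome measures, there were no significant differences observed in terms of the time it took to establish full oral feeding, adverse events". The fourth hypothesis under Material and methods is that infants stimulated by their mothers do no worse on adverse effects.

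Table 3 gives adverse events for D1, D2, D3, D5, and D7 and D14 combined. It has no total, no count of infants with any event and no confidence interval, and its adverse-event rows state no hour.

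**The concern.** A feeding-skill curve can reasonably be sampled at chosen days, because skill on D4 is largely bracketed by D3 and D5. An event count cannot. An event at 17:00, or on a day outside the list, drops out of the comparison even though it was observed. Separate daily counts also cannot be added up to the number of infants affected, because the same infant may appear on several days.

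At stake is the answer to the fourth hypothesis. It is a claim of no excess harm, so it needs the fullest event count available and an interval for the difference. As it stands, it rests on a handful of daily tests on part of the recorded data.

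**Working it through.** **1. Table 3 reproduced.** The printed percentages are shares of the row total (D1: 36/67 = 53.7%), not risks. With 49 and 48 infants as denominators, Fisher's exact test, one-sided in the smaller tail, returns every printed p-value: D1 (36 vs 31) 0.234, D2 (14 vs 14) 0.563, D3 (12 vs 12) 0.570, D5 (2 vs 0) 0.253. The rows therefore behave as counts of infants. Two-sided Fisher gives 0.385, 1.0, 1.0 and 0.495. The Statistical analysis section does not state that tests were one-sided, which is a separate matter.

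**2. Sessions kept.** Inputs: two recordings a day from D1 to full oral feed, and one reading kept on each of D1, D2, D3, D5, D7 and D14 (Data Collection). Time to full oral feed is a median of 10 days in the experimental arm and 9 in the control arm, with IQR 7 to 13 in both (Table 3). For an infant reaching full oral feed on day T, sessions = 2T, and kept = how many of {1, 2, 3, 5, 7, 14} are at most T.

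| T | Sessions | Kept | Left out |
|---|---|---|---|
| 7 | 14 | 5 | 64.3% |
| 9 | 18 | 5 | 72.2% |
| 10 | 20 | 5 | 75.0% |
| 13 | 26 | 5 | 80.8% |
| 14 | 28 | 6 | 78.6% |

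All of this assumes that the rows are 11:00 readings. The D14 coordination row in Table 3 contains all 97 infants. If recording continued to D14 for everyone, 78.6% applies throughout.

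**3. Where the reported events lie.** Both arms together: D1 36 + 31 = 67 of 97, D2 28, D3 24, D5 2, D7 and D14 0. Events cluster early. The unreported slots most likely to hold events are therefore 17:00 on D1 to D3 and both sessions on D4, which lies between 24 and 2.

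**4. How far the share of events depends on what a row is.** The sampled infant-days with an event total 67 + 28 + 24 + 2 = 121, or 1.25 per infant. Assume that D4 lies between the D5 and D3 levels, that D6 is half of D5, and that D8 to D13 are zero.
- Rows are 11:00 readings, and 17:00 resembles 11:00. Missing = 121 + 2×(2 to 24) + 2×1 = 127 to 171. Share captured = 121/248 to 121/292, or 49% to 41%.
- Rows are whole-day counts. Missing = (2 to 24) + 1 = 3 to 25. Share captured = 121/124 to 121/146, or 98% to 83%.

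**5. Infants with any event.** Table 3 only bounds this. Experimental: at least 36 of 49, and at most 49, because 36 + 14 + 12 + 2 = 64 exceeds 49. Control: at least 31 of 48, and at most 48, because 31 + 14 + 12 = 57 exceeds 48. The ranges are 73.5% to 100% and 64.6% to 100%, so the arms cannot be compared on this measure.

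**6. Precision of the daily rows.** Wald 95% intervals, experimental minus control, are −9.4 to +27.2 percentage points on D1 (36/49 vs 31/48) and −17.7 to +16.7 on D3 (12/49 vs 12/48).

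**The case against.** The strongest reply is that the loss of the 17:00 sessions is inferred for adverse events. The restriction is worded to cover every outcome, but that cannot be literal: time to full oral feed is also an outcome, was assessed daily to day 14, and has values such as 9, 10 and 13 that are not among the six days. The adverse-event rows might be whole-day counts. This stands, and it is why no firm figure for missed events can be given.

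Sessions are also a poor yardstick for events. D1 to D3, where events concentrate, are sampled on consecutive days, and nothing was reported on D7 or D14. This stands too, and it narrows the practical gap to the slots named in step 3.

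Three stronger readings are tempting, and the documents do not support them:
- A reader might infer that at least three quarters of sessions are always dropped. That fails for any infant reaching full oral feed before day 10, and the control median is 9.
- A reader might infer that more than half of the events are lost. That needs the 11:00 reading plus the assumptions in step 4.
- A reader might infer that sampling is thinnest just where the arms differ most, because of "D3: Mother performing all steps independently". In Arms and intervention, mothers already perform all stimulation steps on D1 and offer milk on D2; what changes on D3 is supervision. The length of the independent phase is also unclear. The Protocol section gives a 5-day intervention period ending on the third feeding day, whereas Procedure of intervention continues stimulation to full oral feed. On the first reading, 1 of 2 independent sessions is kept; on the second, taken to D14, 4 of 24.

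Finally, the schedule is the same in both arms, so no bias between arms is shown.

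**Conclusion.** The point holds. By its own rule, the analysis sets aside recorded safety data for convenience on an outcome that the Results call primary, and Table 3 cannot show how many infants in each arm had any event. If the rows are 11:00 readings, about 79% of sessions over 14 days are left out, and about 64% to 81% across the IQR of 7 to 13 days if recording stopped at full oral feed. The share of events missed is unknown. The consequence is an incomplete and less precise answer to the fourth hypothesis. Nothing here shows that the comparison would change direction. The criticism concerns what was analysed, not whether infants were monitored.

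**What to change.** - For adverse events, analyse every recorded session from D1 to full oral feed. By arm, report the number and percentage of infants with at least one event, and the events per session with the number of sessions. Give the difference or ratio with a 95% confidence interval that allows for clustering on infant (GEE, or Poisson with robust variance). Label this as added after the six-day results were known, and keep the six-day table as a display.
- State in Table 3 whether each adverse-event row is an 11:00 reading or a whole-day count.
- Reconcile the 5-day intervention period under Protocol with the stimulation period under Procedure of intervention before defining any subset in which mothers act alone.
- If the other sessions' records cannot be retrieved, limit the adverse-event sentence in the Results to the sampled time points.

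The cost is some hours of data entry from records that the document says were made, plus one model. Event counts will probably look higher in both arms. The change does not address the more severe events that led to exclusion, or the infants among the 130 randomised who are not among the 97 analysed.
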